Aim 1. Validating a newly established typology regarding interaction patterns of unstructured symptom discussion in Taiwanese advanced cancer population.

Aim 2: Exploring patients’ experience and thoughts of symptom discussion in regard to their interaction patterns and symptom experience.

Aim 3: Examine relationships between interaction patterns and (a) demographic variables, (b) symptom severity, (c) congruence in symptom assessment between patients/caregivers and providers, (d) patients’/caregivers’ perceived ability to communicate with providers, and (e) patient/caregiver satisfaction.

Procedures

- Recruiting oncologists, patients, and caregivers (collecting demographic information and scheduling an out-patient-department (OPD) visit to be recorded)
- Record 1 OPD visit
- Collect quantitative data: questionnaire measurements
- Schedule an 30-40 minutes interview
- Interview (Incentive will be provided after the interview)
- Analyze the recorded office visit using discourse and conversational analysis: determining interaction patterns
- Analyze the interview using content analysis: exploring patients’ experience regarding the recorded symptom communication
- Analyze quantitative data: the relationship between identified interaction patterns and questionnaire measurements
- Triangulation: compare the results from qualitative interview with the quantitative data to see how the data support or disagree with each other
- Drafting preliminary research report

Figure 2. Research Schema: Conceptual Underpinnings, Study Phases, and Corresponding Specific Aims and Procedures

Methods and Procedures

The method section describes sampling process and study methods of each phase.

Sampling. Because a qualitative study typically requires about 30-50 participants (28), the sample size of this pilot study is set to be 50. The two samples of phase one and two will include the exactly same individuals and same sample size which is about **50 patient/caregiver—physician dyads**, including about 50 patients, 10 physicians, and 50 caregivers, if applicable.

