今天的會談主要想了解您對於上次在診間、被錄音的那次會診的想法或感受。我們的重點尤其會放在當時您在診間溝通症狀時的一些內容；等一下我所問的問題都沒有所謂的正確答案，主要是以您的感覺為主。在開始之前，我很樂意回答您的任何問題。

1. 請回憶上次的會診，您在開始與醫師談話前是否有特別想討論的重點或問題？
2. 告訴我您對這次與醫師談話的任何感受、感想或印象最深刻的的事情。
3. 您與醫師曾討論[所有在診間討論提及的症狀]，請以你的話描述一下當時討論這些症狀的情形。
4. 在討論這些症狀的當下，您的感受是...？
5. 請問您當時還有任何症狀或問題是沒有被提及的嗎？為什麼？請多跟我描述這個[症狀或問題]。
6. 我們發現，您和醫師常以[以簡易方式說明某種互動模式]討論症狀，對於這種互動模式，您的想法或感受是...？
7. 依您的看法，這次的診間談話與平常的診間談話比較起來...？
8. 您覺得這次的談話有什麼優點或是可以改進的地方？

Phase 1: qualitative data collection and analysis. The qualitative phase is a qualitative descriptive study because we want to provide a fundamental and straightforward description regarding the validation of TIPSC (aim 1) and how patients experience and think about the interaction (aim 2).

On the day of the scheduled, audio-recorded office visit, a research assistant will first meet with the patient and caregiver for completing the survey measurements and then accompany them to the office, set up the recording device, and leave. The research assistant will collect the device and recordings after the visit and schedule a follow-up interview between 2 days to a week after the recorded visit. This 30-40 minutes follow-up interview will be conducted by the PI who is a certified oncology nurse with expertise in qualitative study, symptom management, and psycho-oncology. The PI will listen to the recorded visit before interviewing each patient in order to design individual-specific interview questions. Table 2 demonstrates example interview guide. All recorded visits and interviews will be transcribed verbatim.

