Conversation analysis (CA) and discourse analysis (DA) will be used to analyze the transcripts of audio-recorded, naturally occurring OPD conversations as we want to understand patterns of symptom communication and verify the TIPSC (aim 1). CA and DA are selected because they allow us to focus on naturally occurring conversation and what is being accomplished in conversations (29-31). Particularly, CA considers talk-in-interaction as a co-constructive and collaborative process, which fits more with patient-centered and relationship-centered approaches to medical communication (32). CA and DA share similar assumptions and are firstly developed in sociology and linguistics before rapidly evolving in a wide range of disciplines including psychology and social medicine (31). While CA will provide analytic tools to (1) examine the talk turn by turn and (2) look for the related features of patient-provider symptom communication which is a unique sub-type of medical communication (33-36), Goodman's (2017) eight steps of conducting DA will guide the analysis steps of the current study.

Step 1: Deciding Appropriate Research Question. The researchers will focus on aim one which is appropriate for CA/DA because of its action-orientation.

Step 2: Picking Appropriated Data Source. The researchers will analyze naturally occurring OPD conversations which are idea for CA/DA as they are interaction-based.

Step 3: Generating a Corpus. 'Corpus' means 'the collection of all the appropriate data that will be analyzed.' While the researchers plan to record one OPD visit for 50 patient/caregiver—physician dyads, only conversations which contain discussions of symptoms will be included and analyzed.

Step 4: Transcribing Data. The data are primarily transcribed according to the conventions developed by Jefferson (37, 38), with slight modifications to those inapplicable to Mandarin Chinese characters. Jefferson's transcription conventions make it possible to capture the details of the talk—not only what was said, but also the way it is said. Pauses, rising/lower volume, or the change of intonation will be noted. Remarks on other verbal sounds—such as coughing and clearing throat—will be provided in italics inside double parentheses. The following software will be used to assist data transcription: Speechnotes, ELAN, and InqScribe.

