This spate of talk constitutes a prototypical turn-taking organization of doctor-patient communication—doctors posing questions and patients answering. The doctor’s turns are compositionally complex than the patient’s but relatively straightforward; the patient provides (negative) minimal responses. The turn organization represents a course of checklist symptom inquiry with patient indicating no problem. The doctor’s questions are all designed as yes-no questions in different syntactic formats with different lexical choices. All the questions communicate an expectation in favor of ‘no’ responses. The preference for ‘no’ answers is enforced by the use of the lexical item ‘any’ (instead of ‘some’) and ‘no’. Through an intervention study, it is shown that such question designs may lead to unmet concerns in office visits.

Step 7: Building a Case to Support the Findings. Similar to table one which was established in the preliminary study, the researchers refine definitions and pick best exemplars to describe each interaction patterns.

Step 8: Report Writing. Final research report and manuscripts will be established in this stage.

The standard content analysis will be used to analysis the follow-up interview because we want to provide a fundamental and low-interpretive description of how patients experience the

symptom discussions (42).

Phase 2: Quantitative data collection and analysis. The quantitative phase employs a correlational design because the aim of this phase is to examine the relationships between interaction patterns and variables including demographic variables, symptom severity, congruence in symptom assessment between patients/caregivers and physicians, patients' perceived ability to communicate with physicians, and patient/caregiver satisfaction (aim 3).

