Patients' perceived ability to communicate with providers will be measured by **Perceived Efficacy in Patient-Physician Interactions Scales (PEPPI-10, Chinese version)**. PEPPI-10 is a self-evaluated, 10-item instrument measuring patients' self-efficacy in "obtaining medical information and attention to their medical concerns from physicians (46)." Patients rate their confidence of interacting with physicians (e.g., get a doctor to pay attention to what you have to say) from "no confident (0)" to "extremely confident (10)". The Chinese version of PEPPI-10 shows good validity and reliability with the reported Cronbach's α coefficient of 0.907 (47).

Patients' overall satisfaction will be measured by the **Chinese Patients' Satisfaction Scale (C-PSS)**. C-PSS is a 27-item instrument which was developed to measure Chinese patients' satisfaction using a 5-point Likert scale. Patients rate their satisfaction from strongly disagree (1) to strongly agree (5) with higher scores represent better satisfaction. It is a reliable and valid tool with the reported Cronbach's alpha coefficient of all dimensions above 0.90 (48).

The major interaction patterns or combination of interaction patterns will be determined and dummy coded. Binomial Logistic Regression will be used to examine the relationship between interaction patterns and dichotomous variables (i.e., the congruence of symptom reports) while Linear Regression will be applied to examine the relationship between the interaction patterns and other variables, such as age, level of symptom severity, perceived communication ability, and satisfaction. The SPSS software will be used to organize the data and facilitate data analysis. Finally, combining and comparing the findings from the interviews and the results from the quantitative measurements enable us to do triangulation to fully map up the interaction behavior pertinent to symptom discussion.

Trustworthiness

To ensure the quality of study results and conclusions, five standards outlined by Miles and colleagues (2013) will serve as an evaluative framework. The standards are **confirmability, reliability, credibility, transferability, and utilization**.

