All data will be de-identified by using heuristic methods. Electronic data will only be send using NTU or NTUH email system and be stored in the secure space at the network-attached storage system which can only be accessed with assigned username and password. Written information will be locked in PI's office at National Taiwan University.

	Year	2018		2019				2020				2021	
	Months	9	10-12	1-3	4-6	7-9	10-12	1-3	4-6	7-9	10-12	1-3	4-7
Phase 0. Obtain IRB approval		x											
Phase 0. Obtain questionnaire measurements		x											
Phase 0. Establish research team		x											
Phase 0. Recruit oncologists & patients			x	x	x								
Phase 1. Record 1 OPD visit & collect questionnaire measurements			x	x	x								
Phase 1. Interview				x	x	x							
Phase 1. Analyze recorded office visits					x	x	x	x	x				
Phase 1. Analyze interviews					x	x	x	x	x				
Phase 1. Check study trustworthiness: request selected participants' feedback on qualitative results									x	x			
Phase 2. Analyze quantitative data based on qualitative findings of recorded OPD visit									x	x	x		
Phase 2. Compare the qualitative findings of interview with the quantitative data (triangulation)										x	x	x	
Phase 2. Check study trustworthiness: request international experts' feedback on final results												x	
Phase 2. Report and Manuscript writing												x	x

*Abbreviation: Out-patient-department (OPD)

	Expecting direct research results	Expecting indirect process results
YEAR 1 (2018, 9—2019, 7)	
 ▪ Obtaining IRB approval ▪ Obtaining questionnaire measurements ▪ Finishing the recruitment of oncologists and patients 	
 ▪ Establishing research team: recruit members and establish regular meetings ▪ Training: recruitment strategies and research methodology (mixed-methods), interview skills ▪ Presenting methodology at local/national/international conferences ▪ Online international collaboration: study design
YEAR 2	
 ▪ Finishing collection of qualitative data: recorded 	
 ▪ Identifying and securing international collaboration opportunities

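### Does Phase 2 need a stated rule for recorded visits in which no symptom is discussed?

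*Combined protocol and SAP*

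**What the plan says.** The Sampling paragraph under Methods and Procedures sets one size, about 50 dyads, for both phases: "The two samples of phase one and two will include the exactly same individuals and same sample size". Step 3 (Generating a Corpus) says that "the researchers plan to record one OPD visit for 50" dyads, and then that "only conversations which contain discussions of symptoms will be included and analyzed". Steps 5 and 6 assign typology patterns within that corpus.

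Phase 2 builds on the result. Figure 2 lists the task as "Analyze quantitative data: the relationship between identified interaction patterns and questionnaire measurements", and the timeline (Table 3) as "Analyze quantitative data based on qualitative findings of recorded OPD visit". The Phase 2 analysis paragraph adds: "The major interaction patterns or combination of interaction patterns will be determined and dummy coded". It then names binomial logistic regression for congruence of symptom reports and linear regression for the other variables.

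None of these places states how a recorded dyad outside the corpus is handled in the regressions, or that recruited, recorded and coded dyads are tallied separately.

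**The concern.** Step 3 allows for a corpus smaller than the set of recordings, while the Sampling paragraph gives both phases the same people and the same number. A dyad whose visit contains no symptom talk completes its questionnaires but receives no pattern. On paper it could be dropped, given a category of its own, or left at zero on every dummy variable.

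The last option would do harm, because the dyad would merge silently with the reference pattern. With eight patterns spread evenly over 49 coded dyads, the reference group holds 49/8 = 6.1. One stray dyad added to it would carry 1/7.1 = 14% of the reference mean.

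Dropping such dyads raises a milder question. It selects on symptom talk, which may be related to severity, congruence and satisfaction. The pilot is also meant to supply parameters for larger studies, so a reader might want to know how many recorded visits yield a codable pattern.

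**Working it through.** **Side by side.** Step 3 decides what is analysed. Steps 5 and 6 give patterns only to what is analysed. Figure 2 and Table 3 make those patterns the input to Phase 2, and the Phase 2 paragraph dummy codes them. A visit outside the corpus therefore has no exposure value. An all-zero row would contradict Step 3, and nothing in the text suggests one. The Sampling sentence can be read as describing who is enrolled, and on that reading it does not conflict with Step 3.

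**Which visits are affected.** Only those in which no symptom is raised or asked about. A visit with questions and denials still has a pattern: of its example of that kind, Step 6 says "The turn organization represents a course of checklist symptom inquiry with patient indicating no problem". Eligibility excludes patients without symptoms, and the Background calls symptoms often the major topic of these conversations.

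**The plan's own figure.** The 50 is the upper end of a 30–50 rule of thumb for qualitative work. The documents give no alpha, power, effect size or dropout, so no formula reproduces it and losing a few dyads breaks no stated calculation.

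**Likely number.** Let q be the share of recorded visits with no symptom talk. The documents do not give q, so every value here is assumed.

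- Expected count = 50q.
- Chance of at least one, independent dyads = 1 − (1 − q)^50.
- Chance of at least one, clustered = 1 − [B(a, b+5)/B(a, b)]^10, with a = 9q and b = 9(1 − q). This takes 10 physicians (Sampling paragraph) with 5 patients each and an assumed intraclass correlation of 0.1.

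| q | Expected of 50 | At least one, independent | At least one, clustered |
|---|---|---|---|
| 0.5% | 0.25 | 22% | not computed |
| 1% | 0.5 | 39% | 34% |
| 5% | 2.5 | 92% | 88% |
| 10% | 5 | above 99% (0.9^50 = 0.005) | not computed |

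**Cost in precision.** The standard error factor is √(50/n).

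- n = 49: √(50/49) = 1.010
- n = 48: √(50/48) = 1.021
- n = 45: √(50/45) = 1.054

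The detectable correlation is tanh[(1.960 + 0.842)/√(n − 3)], assuming two-sided 5%, 80% power and no clustering. It is 0.387 at n = 50, 0.395 at n = 48 and 0.407 at n = 45.

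**Recoverability.** The number of such visits is recorded visits minus corpus visits. Both are known to the team, and the interview procedure already requires that "The PI will listen to the recorded visit before interviewing each patient".

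**The case for a change.** The strongest case for a change is that exclusion is inferred and never stated. Read literally, the Sampling sentence could lead an analyst to keep all 50 dyads. Such visits are also possible on the study's own account: the Background reports that patients lack the chance or the motivation to raise severe symptoms, and the interview guide (Table 2, item 5) asks about symptoms that went unmentioned. Stating the rule and reporting three counts would cost little. If 50 dyads were recruited, 45 recorded and 43 coded (illustrative figures), 7/50 = 14% of recruited dyads would lack a pattern, but only 2/45 = 4.4% of recorded visits would have gone uncoded.

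Part of this stands. The rule is not written down in the text available, and the promises under Trustworthiness to document the analysis and describe participants are general. Three things weaken the rest.

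- The three counts would not isolate visits without symptom talk. A recorded dyad can also be uncoded because the recording is unusable or because no major pattern is assigned.
- The passage on parameters for larger studies concerns power and sample size drawn from relationships between patterns and outcomes. It does not name the yield of codable visits.
- The selection point does not bias what Aim 3 asks. Aim 3 compares patterns of symptom discussion, so visits that contain such discussion are its natural population. It does not compare discussed with not discussed.

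**Conclusion.** No change to the plan is called for. This is missing detail that any analyst would fill in the same way: a dyad with no interaction pattern cannot enter a regression on interaction patterns. Writing the rule down would leave the aims, the corpus, the models and the estimates as they are. The number analysed will be apparent when the regressions are reported.

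The size is slight. Over the assumed 0.5% to 10%, at most about 5 of 50 dyads are expected to drop out, and standard errors rise by no more than about 5% (45 coded dyads). The true share may be near zero; at 1% the chance that no such visit occurs is 0.99^50, about 60%.

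The conclusion rests on reading the Sampling sentence as enrolment and on the assumed shares. It is also limited by what could be read: Figure 3, which covers recruitment and data collection, and most of Table 1 were not available, so the plan may say more than is visible here.

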Among the multiple aspects of healthcare that can be affected by communication, **symptom management is one of the critical outcomes of patient—provider communication** (13-15). Indeed, symptom, perceived indicators of change in normal functioning as experienced by patients (16), is often the major topics of cancer patient—provider communication (17). In Taiwan, cancer remains the leading cause of death since 1982. It was estimated that there were more than 103 thousand newly diagnosed cancer patients in 2014 with considerable portion of them diagnosed with advanced stages (i.e., stage III or IV)(18). **While symptom management is one of the primary care goal for these advanced cancer patients, the quality of symptom communication is beyond satisfactory**. Cancer patients had either no chance to talk about or low motivation to discuss their severe symptoms (19-21). A study done in Taiwan have further revealed that the “fear of distracting the doctor” was a main barrier for cancer patients to report the symptom of fatigue (22). The ineffective symptom communication may prevent healthcare providers (HCP) from conducting accurate symptom evaluation and effective management. For example, HCP tended to underestimate patients’ symptoms which shows the incongruence of symptom evaluation between patients and HCP (23). Despite the poor quality of symptom communication, there is a lack of systematic and comprehensive understanding regarding patient—provider symptom communication. Specifically, few studies have considered (1) the theoretical underpinnings, (2) naturally occurring medical encounters, and (3) both patients’ and providers’ communication behavior. **In fact, to date, no published study exploring advanced cancer patient—provider symptom communication in Asia countries. Studies which explore symptom communication thoroughly is thus much-needed in order to fully map out and facilitate symptom communication in Taiwan.**

Purpose and Specific Aims

The purpose of this mixed methods study is to **provide an enrich and systematic description of symptom communication by validating a typology of interaction patterns regarding symptom communication (TIPSC) between patients with advanced cancer and their healthcare providers (HCP) and exploring factors related to each interaction pattern**. The specific aims are to:

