1. Validate TIPSC in Taiwanese advanced cancer population in terms of how patients, caregivers, and HCP discuss symptoms during out-patient-department (OPD) visits.
2. Explore patients’/caregivers’ experience and thoughts of symptom discussion in regard to their interaction patterns and symptom experience.
3. Examine relationships between interaction patterns and (a) demographic variables: age and educational level, (b) symptom severity, (c) congruence in symptom assessment between patients/caregivers and HCP, (4) patients’/caregivers’ perceived ability to communicate with

HCP, and (5) patient/caregiver satisfaction.

Conceptual Underpinnings

The specific aims and research design of this proposed study are informed by two conceptual frameworks. **Aim one and two which seek to deductively explore interaction patterns of symptom communication are informed by a typology, TIPSC, developed by the applicant.** The applicant used qualitative methods to explore naturally occurring symptom discussions to establish this typology that describes eight interaction patterns of advanced cancer patient—provider symptom communication. These eight interaction patterns which reflects unique style of symptom communication are collaborative, explanatory, agentic, checklist, cross-purpose, empathic, admonishing, and diverging interactions (24). The definitions and exemplars of each interaction pattern are presented in table 1. Building on this typology developed in the U.S., the proposed study seeks to explore and categorize symptom communication in Taiwanese cancer population and, at the same time, verify or even expand the TIPSC. Once the qualitative verification of the TIPSC is established, we are able to quantitatively examine the relationship between interaction patterns and meaningful variables or outcomes which lead to our specific aim three.

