There are three steps of recruitment processes. First, physicians who are currently in clinical practice at National Taiwan University Hospital and care for patients with solid tumors will be recruited through study presentations at grand rounds, meetings, or personal contacts. A research assistant then meets with interested physicians for explaining the details of the study, consenting, and setting up following schedules for recruiting patients at OPD visits. Second, research assistants identify potential eligible patients by working closely with participating physicians and their clinic nurses. These potential eligible patients will be approached by their physicians, nurses, or research assistants. We include patients who are: (1) currently a patient of a participating physician, (2) diagnosed with advanced solid cancer (TNM stage III or IV), (3) aged 20 years or older, (4) able to tolerate an interview that will last approximately 30 minutes, and (5) able to speak Chinese or Taiwanese. Patients who (1) do not experience any symptoms, or (2) are hospitalized at recruitment are excluded. Finally, caregivers who will participate in the OPD visits with participating patient will be approached. Caregivers who are younger than 20 years old or cannot speak Chinese or Taiwanese will be excluded.

Recruitment process. Interested patients and their caregivers will receive a pamphlet regarding study information when research assistants explain study process, confirm participation, and arrange schedules. Signed written consents will be obtained from physicians, patients, and caregivers before data collection. Participated patients and caregivers are required to (1) provide an audio-recorded, unstructured OPD visit with their physicians, (2) complete 3 survey measurements (European Organization for Research and Treatment of Cancer, Perceived Efficacy in Patient-Physician Interactions scale, and The Chinese Patients' Satisfaction Scale), and (3) participate in a 30-40 minutes interview at home or a private room. On the other hand, participated physicians will complete European Organization for Research and Treatment of Cancer immediately after the recorded OPD visit. Figure 3 represents the recruitment and data collection process.

[figure not shown]

Fig 3. Recruitment and Data Collection Process

Table 2. Example Interview Guide (Patient version)

*[] 中文字會視每位病人在診間與醫師的對話內容而更動

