In addition to demographic information, three questionnaire measurements: **European Organization for Research and Treatment of Cancer (EORTC-QLQ C30)**, **Perceived Efficacy in Patient-Physician Interactions scale (PEPPI)**, and **The Chinese Patients' Satisfaction Scale (C-PSS)** will be used to collect data regarding symptom severity, perceived ability to process the information, and overall satisfaction, respectively. The oncologists are required to provide their own demographic information and EORTC-QLQ ratings after seeing each participated patient. Patients are required to provide information of demographic data, EORTC-QLQ C30, PEPPI, and Satisfaction scale. The demographic information will be collected at the time of recruitment while other questionnaires will be collected after the recorded office visits. More information regarding each questionnaire measurements are described below.

Symptom severity will be measured by **European Organization for Research and Treatment of Cancer (EORTC-QLQ C30, Taiwan Chinese version)**. The EORTC QLQ-C30 is a 30-item questionnaire developed by a group of scientists to evaluate functions, symptoms, and overall health-related quality of life of cancer patients. EORTC QLQ-C30 has been verified and widely applied in health-related research. Evaluators rate patients' functions, symptoms, and quality of life using 4-point Likert scales. The Taiwan Chinese version of the EORTC QLQ-C30 has been tested and shows good reliability and validity (43, 44). The reported Cronbach's alpha coefficient of most items was above 0.70 across studies. A 5-10—points difference of EORTC QLQ-C30 rating is considered a significant difference (45). That is, if the difference of EORTC QLQ-C30 rating between a patient/caregiver and a physician is greater than 5, it is defined as an incongruence symptom report.

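### The QLQ-C30 congruence rule (difference above 5) leaves metric, scores, sign and combining rule open, does not settle whose rating counts, and discards the size of the gap

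*Combined protocol and SAP*

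**What the plan says.** Under Phase 2: Quantitative data collection and analysis, the plan describes a 30-item instrument on which evaluators rate functions, "symptoms, and quality of life using 4-point Likert scales". It cites a range of 5 to 10 for which a "points difference of EORTC QLQ-C30 rating is considered a significant difference", and from this derives its rule: a difference that "between a patient/caregiver and a physician is greater than 5, it is defined as an incongruence symptom report". The analysis paragraph of the same section names congruence as the dichotomous variable for binomial logistic regression. Symptom severity, perceived communication ability and satisfaction go to linear regression.

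The sections differ on who rates:
- Recruitment process: "Participated patients and caregivers are required to (1) provide an audio-recorded, unstructured OPD visit with their physicians, (2) complete 3 survey measurements", and the QLQ-C30 is one of the three.
- Phase 2: "Patients are required to provide information of demographic data, EORTC-QLQ C30, PEPPI, and Satisfaction scale". Caregivers are not mentioned there. Oncologists rate each patient after the visit.
- Sampling: the sample is described as "including about 50 patients, 10 physicians, and 50 caregivers, if applicable".

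They also differ on timing. The Phase 1 section has the patient and caregiver complete the surveys before they enter the recorded visit. The Phase 2 section collects them afterwards.

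Aim 3 lists "congruence in symptom assessment between patients/caregivers and HCP" among its variables, and Conceptual Underpinnings treats congruence as one of two communication outcomes. The Background section illustrates incongruence by direction: "For example, HCP tended to underestimate" patients' symptoms.

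**The concern.** The rule is the whole definition of an Aim 3 outcome, and an analyst cannot apply it without making choices that the plan does not record: raw or 0-100; symptom scores only or all scores; patient minus physician or absolute difference; one score or several, and if several, how they become one yes/no. The raters are named, but patient/caregiver is not resolved for a dyad in which both complete the form. Two analysts could derive different outcomes from the same questionnaires.

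The yes/no split then loses information in a sample of about 50 dyads. It loses the size of the gap and, if the difference is taken as absolute, also its direction, which is the feature the Background section describes. The timing conflict adds to this: a patient rating made before the visit would be set against a physician rating made after the communication under study. Expecting Results says the findings can be used to size larger studies, so an undefined outcome may carry forward.

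**Working it through.** **Inputs from the documents.** 4-point items; cut-off above 5; about 50 dyads and 10 physicians. The plan gives no incongruence rate, significance level or power, so there is no figure of its own to reproduce.

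**1. Raw metric.** The largest gap on one item is 4 - 1 = 3, so a difference above 5 cannot occur. A mean of raw items is also bounded by 3. A raw sum of k items has a largest gap of 3k. For k = 2 that is 6, so the rule is met only if both items are at opposite ends in the same direction.

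**2. 0-100 metric (assumed; the 5-10 point range suggests it).** The smallest possible gap on a k-item score is 100/(3k):

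| Items k | 1 | 2 | 3 | 4 | 5 | 6 | 7 |
|---|---|---|---|---|---|---|---|
| One step (points) | 33.3 | 16.7 | 11.1 | 8.3 | 6.7 | 5.6 | 4.8 |

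Up to six items, one step already exceeds 5. The rule then separates equal from unequal scores, and a one-category gap on a single item (33.3) counts the same as a three-category gap (100). From seven items on, at least two steps are needed and the cut-off does discriminate.

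**3. Cost of dichotomising (illustration).** Assumptions: 0-100 scoring; response shares 40/30/20/10%; latent-normal items with within-score correlation 0.6; five scores correlated 0.3; 1, 2 or 3 items per score; two pattern groups of 25 independent dyads; two-sided 5% tests. The continuous outcomes use linear regression and the yes/no rules use a logistic likelihood-ratio test. The three absolute rules call a dyad incongruent if any, most or all of the scores differ by more than 5. Ranges run over 1-3 items.

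| Contrast between groups | Continuous | Best absolute yes/no rule |
|---|---|---|
| Rater correlation 0.9 v 0.8, mean absolute difference | 46-64% | 22-31% |
| Rater correlation 0.9 v 0.6, mean absolute difference | 98% to over 99% | 59-79% |
| One score only, 0.9 v 0.8 | 14-19% | 12-14% |
| One score only, 0.9 v 0.6 | 48-63% | 28-37% |

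For 1, 2 and 3 items the first row is 46 v 25%, 59 v 31% and 64 v 22%.

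**4. Direction.** Same model, rater correlation 0.8 in both groups, physicians in one group rating lower:

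| Physician shift | Signed mean, continuous | Signed mean above 5, yes/no | Absolute mean, continuous | Best absolute yes/no rule |
|---|---|---|---|---|
| about 7 points | 48-61% | 37-46% | 5-6% | 6-9% |
| about 14 points | 95-99% | about 85-94% | 12-25% | 8-10% |

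At 7 points the absolute difference does no better than its 5% false-positive rate. Conversely, when groups differ only in rater correlation, the expected signed difference is the same in both, so the signed outcome cannot detect that contrast. Neither outcome replaces the other.

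**5. Unequal groups.** With 10 v 40 dyads and HC3 robust errors, at 0.9 v 0.8 either way round, power is 27-50% continuous against 17-21% for the best absolute yes/no rule. With rater correlation 0.6 in the group of 10, 0.9 in the group of 40 and no shift, the signed test rejects falsely in 16-17% of samples with ordinary errors and in about 6% with HC3.

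**The case against.** The strongest reply has four parts.

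- **The wording may mean one score.** The plan speaks of a rating in the singular. If one score is meant, no combining rule is needed, and for a short score with a small contrast dichotomising loses little (14-19% v 12-14%). This stands as a limit on the size of the loss. It does not supply the metric, the score or the sign.
- **The rule can be read as signed.** A reader might infer that every reading throws direction away. The text does not support that: it sets no absolute value, and patient minus physician above 5 is an equally literal reading that keeps direction. On that reading the yes/no rule reaches 37-46% at a 7-point shift, not far below the continuous signed difference and well above the absolute one. The defect is that the sign is unstated.
- **The raters are named.** A reader might infer that no rater is specified. In fact patient/caregiver and physician are both in the rule. What is missing is a choice when patient and caregiver both rate, together with agreement between Recruitment process and Phase 2.
- **This is a pilot.** The design section gives priority to the qualitative part, and Sampling sets 50 on qualitative grounds. Congruence is one of five Aim 3 variables, and linear over logistic is partly preference. This bears on severity and stands.

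Two further limits apply. For scores of two to six items, equal scores are not exact agreement, because item disagreements can offset each other. And every power figure assumes independent dyads, whereas 50 dyads among 10 physicians is about 5 each; HC3 errors do not address that.

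**Conclusion.** The point holds as a should-fix. From the documents' own 4-point format, the rule is impossible on one raw item. Under an assumed 0-100 metric it means unequal scores for any score of six or fewer items. Which of these applies is not stated, nor are the scores, the sign or the combining rule. Keeping the difference continuous is a better use of the same data when several scores are combined, and of modest benefit for one short score with a small contrast. The power figures are illustrative and rest on the assumed response shares, correlations, group sizes and independence.

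A reader might also infer that the missing combining rule alone moves the incongruent share from 2% to 92% in this trial. The documents do not support that. Those are the all-scores and any-score extremes for five one-item scores at an assumed rater correlation of 0.8; most-scores gives 35%. With three items per score the extremes become 18% and 99%. They show that the rule matters, not what the trial would find.

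**What to change.** In the Symptom severity paragraph of Phase 2, replace the cut-off sentence with a definition that states:

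- QLQ-C30 symptom scores are expressed on 0-100, and the scores compared are listed by name.
- Patient and physician are compared in every dyad; any caregiver-physician comparison is made the same way and reported separately.
- Congruence is analysed as two continuous outcomes of equal standing: the mean signed difference (patient minus physician) for direction, and the mean absolute difference for size.

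In the analysis paragraph, move congruence to the linear regression already planned, with heteroscedasticity-robust standard errors because pattern groups may be unequal. If a yes/no rule at 5 is kept, make it a secondary descriptive only. State its metric, sign and combining rule, and note that on scores of six or fewer items it means equal versus unequal scores.

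Reconcile Recruitment process, Phase 1 and Phase 2 on whether caregivers complete the QLQ-C30 and whether the surveys come before or after the recorded visit.

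Cost: wording in those sections; no new forms. The downsides are mean differences instead of odds ratios, two outcomes instead of one, skewed absolute differences, and averaging that may dilute a large gap on one symptom.
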